## 7.1.1.2.3 Fluid (Plasma, CSF) and PET Imaging (Amyloid and Tau) Biomarker Data

Analysis visit windows for the biomarker parameters are defined in a similar manner as those for the efficacy parameters. Biomarker data will be allocated to analysis visits corresponding to the analysis visit window intervals in which they fall in as specified in Table 7-15 to Table 7-19.

Table 7-15. Analysis Visit Windows for PD Plasma Biomarker Assessments

Analysis Visit	Target Day	Analysis Visit Window (Based on Study Day)
Baseline	1	≤ 1
Week 1	8	[2, 12]
Week 2	15	[13, 22]
Week 4	29	[23, 36]
Week 6	43	[37, 50]
Week 8	57	[51, 71]
Week 12	85	[72, 99]
Week 16	113	[100, 141]
Week 24	169	[142, 211]
Week 36	253	[212, 295]
Week 48	337	[296, 379]
Week 60	421	[380, 463]
Week 72	505	[464, 547]
Week 84	589	[548, 631]
Week 96	673	≥ 632

Table 7-16. Analysis Visit Windows for CSF Biomarker Assessments

Analysis Visit	Target Day	Analysis Visit Window (Based on Study Day)
Baseline	1	≤ 1
Week 6	43	[2, 190]
Week 48	337	[191, 421]
Week 72	505	[422, 589]
Week 96	673	≥ 590

Protocol No. AL002-2 Last Revision Date: 12 Aug 2025

Table 7-17. Analysis Visit Windows for Amyloid PET Assessments

Analysis Visit	Target Day	Analysis Visit Window (Based on Study Day)
Baseline	1	≤ 1
Week 48	337	[2, 505]
Week 96	673	≥ 506

Table 7-18. Analysis Visit Windows for Tau PET Assessments, True Baseline\*

Analysis Visit	Target Day	Analysis Visit Window (Based on Study Day)
Baseline	1	≤ 1
Week 48	337	[2, 421]
Week 72	505	[422, 589]
Week 96	673	≥ 590

\*True baseline: baseline corresponds to the pre-dose visit (prior to dosing).

Table 7-19. Analysis Visit Windows for Tau PET Assessments, Redefined Baseline (Sensitivity Analysis)\*

Analysis Visit	Target Day	Analysis Visit Window (Based on Study Day)
Baseline_R	1	≤ Day 1 Predose, if it exists. If not, then day of Week_R 48 nonmissing result (up to Day 421)
Week_R 48	337	[2, 421]
Week_R 72	505	[422, 589]
Week_R 96	673	≥ 590

\*Redefined baseline: baseline corresponds to either the pre-dose visit (prior to dosing) if the pre-dose Tau PET scan is evaluable, or 1st postdose visit if the pre-dose Tau PET scan is missing.

Protocol No. AL002-2 Last Revision Date: 12 Aug 2025

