1.4. AL002 Dosage Determination

In this Phase 2 study, eligible participants with Early AD (Refer to Section 1.5 for definition of Early AD) will each receive 1 of the following 4 treatments: placebo, 15 mg/kg AL002, 40 mg/kg AL002, or 60 mg/kg AL002.

The doses selected for this Phase 2 study are based on the clinical experience during the dose-escalation Phase 1 study conducted in healthy volunteers (Study AL002-1). Population pharmacokinetic and pharmacodynamic modeling has been performed on the preliminary data from Study AL002-1. Dose-response outputs from the model support dosing with 15 mg/kg, 40 mg/kg, and 60 mg/kg in the Phase 2 study.

Based on simulations of serum concentrations of AL002, the 75th percentile for 15 mg/kg is lower than the 25th percentile for 40 mg/kg. The 40 mg/kg and 60 mg/kg simulations are closer together with the 75th percentile from 40 mg/kg being close to the median for 60 mg/kg. Simulations of concentrations of AL002 in the CSF produced similar results.

Based on simulations of the target engagement marker sTREM2 in CSF, the 75th percentile for 15 mg/kg is slightly higher than the 25th percentile for 40 mg/kg. The simulations for 40 mg/kg and 60 mg/kg suggest that a similar effect on sTREM2 may be seen for these 2 doses. Based on these simulations sTREM2, the predication is that downstream biological activity will be similar for the 40 mg/kg and 60 mg/kg dose levels, with a somewhat higher likelihood of activity for the highest dose level at 60 mg/kg.

A 15 mg/kg dose is considered a low dose, but one that has an effect on sTREM2 in the brain and that could still provide benefit. The 40 mg/kg dose is currently predicted to provide a similar effect on sTREM2 compared to the 60 mg/kg dose, but with lower exposure. The 60 mg/kg dose will provide a higher exposure and PK/PD data in participants should 40 mg/kg not provide sufficient clinical benefit. Testing these doses in the current Phase 2 study is expected to provide adequate information for selecting the dose for subsequent Phase 3 studies.

PK in serum of the healthy volunteers of Study AL002-1 is characterized by a terminal half-life of 9.0 days at an IV dose of 15 mg/kg and 9.1 days at an IV dose of 60 mg/kg. C_{max} and total AUC (AUC $_{inf}$) were generally dose proportional. For additional information regarding PK data in these cohorts, please refer to Section 5 of the IB.

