3.3.4. Follow-Up Visits

When a randomized participant completes all study visits and procedures up to and including the final visit of their planned treatment period, an SFU visit will follow 8 weeks after this last treatment period visit, unless the participant enrolls in the AL002-LTE study. The end of a given participant's planned treatment period is defined by the TPTD as noted above. For participants who had paused dosing or who had prematurely discontinued dosing, the TPTD as noted above, will still define the end of their planned treatment period. The SFU visit will follow 8 weeks after the end of the planned treatment period for each participant, unless the participant enrolls in the AL002-LTE study. If a participant enrolls in the AL002-LTE study, an SFU visit is not required.

An EFU visit may or may not be required for a given participant, who has completed the planned treatment period and does not enroll in the AL002-LTE study. If a participant enrolls in the AL002-LTE study, an EFU visit is not required. For participants who do not enroll in the AL002-LTE study, an EFU visit is required 4 weeks prior to the SFU visit if the final COA and biomarker assessments were not completed within the defined time intervals as follows:

- An EFU is required if the last COA visit was done more than 12 weeks since the date the EFU visit would occur.
- An EFU visit is required if the last LP was done more than 12 weeks since the date the EFU visit would occur.
- An EFU is required if the last Amyloid PET or Tau PET was done more than 24 since the date the EFU visit would occur.

If the COA, LP, or PET biomarker assessments were not collected in the specified time period noted above, the participant will need to complete an EFU visit 4 weeks prior to the SFU visit.

An ET visit is performed only in cases where participation is permanently discontinued. If the participant withdraws or is discontinued from the study for any reason, the ET is completed 8 weeks after the last administered dose. Participants who complete an ET visit will not require a SFU visit, if the safety assessments were collected at a regularly scheduled study visit 8 weeks after the final dosing visit. Similarly, to the EFU visits for those who have completed the planned treatment period, the following efficacy and biomarkers are required as part of the ET visit if the following conditions are met:

COA visit was done more than 12 weeks since the date the ET visit would occur.

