Study drug administration			X		x	х	X	х	х	x	х	x	X	X	X	X	х	x	X	x	х	X	х	X	х	х			
Adverse events ^{j,q}	X	$\mathbf{x}^{\mathbf{k}}$	х	Х	х	х	xrr	х	х	Х	х	X	х	х	х	х	х	х	х	X	х	X	X	X	X	х	\mathbf{x}^{l}	х	Х
ECG (triplicate) ^{j,r,pp}	X		х		х		х			Х						х							X					х	
Pregnancy test (if applicable) ^s	X	$\mathbf{x}^{\mathbf{k}}$														$\mathbf{x}^{\mathbf{k}}$					$\mathbf{x}^{\mathbf{k}}$						x ^t	x ^t	\mathbf{x}^{t}
Thyroid function	Х																												
Folic acid and vitamin B12 levels	х																												
Hematology ^{h,u} and chemistry ^{h,v}	х		х				х				х			Х			х						х					x	x
Coagulation ^{h,w}	Х														х					x ⁿⁿ									Х
Urinalysis ^{h,x}	Х		х								х						х						х					х	X
C-SSRS ^h			Х							х						х					х		X			Х	x ^y	х	x ^y
MRI (safety, PD) ^{h,ll}	xz				х	х	х			Х						х					х					Х			
$CDR^{h,aa}$	Х									Х						х					х					Х	x ^y		x ^y
MMSE ^{h,aa}	Х									х						х					х					Х	x ^y		x ^y

AL002 Alector, Inc.

Table 9: Schedule of Assessments – Part 1 (Study Week 9 and Following) and Part 2 (All Visits) (Continued)

Study Period	Screening (Days -78 to -23) ^{ss}	Predose Baseline (Days -22 to -1)											Т	`reat	ment													1 p	
Study Week ^a			1 (D1)	3 (D15)	5 (D29)	9 (D57)	13	17	21	25	29	33	37	41	45	49	53	57	19	65 and 69	73	77	81	85	89 and 93	76	EFU/4 weeks ^{qq}	SFU/8 weeks ^d	ET
Visit Window ⁰⁰			p ⊊∓	±5d	±5d	±5d	p ⊊∓	p ⊊∓	±5d	p ⊊∓	₽ 2∓	±5d	±5d	±5d	p ⊊∓	p ⊊∓	p⊊∓	p⊊∓	p ⊊∓										
		Part	2 onl	y	•								For	parti	cipar	its ra	ndo	mize	d un	der P	arts	1 an	nd 2					•	
ADAS-Cog13 ^{h,aa}			x							х						X					х					Х	xy		x ^y
RBANS-Updateh,aa	х									х						x					х					Х	xy		x ^y
ADCS-ADL-MCI ^{h,aa}			x							X						X					х					х	x ^y		x ^y
Serum PK sample(s) ^{j, bb}			х	Х	х	х	х	х		х			х			x			х		х			x		Х		х	Х
Serum sample for ADA ^{h,bb}			X	x		X		X		X			X			X			x		х			x		х		x	X
Plasma sample for PD biomarkers ^h	x		X	X	X	X	X	X		x			X			X			х		х			x		x		x	X
PrecivityAD TM -Aβ blood test ^{kk}	x																												
Whole blood sample for mRNA ^h			х	х						х						х										х			х
Blood sample for WGS ^h			х																										
APOE e4 testing	х																												
Whole blood sample for other targeted genomic variants ^{h,cc}			x																										

AL002 Alector, Inc.

Table 9: Schedule of Assessments – Part 1 (Study Week 9 and Following) and Part 2 (All Visits) (Continued)

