#### 6.2.1.2 Primary Estimand for Primary Efficacy Endpoint

- Treatment condition: while on study treatment regardless of other interventions.
- Target population: adult participants with early AD, excluding APOE e4/e4 participants as defined by the protocol inclusion/exclusion criteria.
- Primary endpoint: CFB in CDR-SB score to Weeks 24, 48, 72, and 96.
- Accounting for intercurrent events: a composite strategy will be used to handle intercurrent events as below:
  - Hypothetical strategy for handling premature study drug discontinuation for any reason (data will be considered missing after a participant prematurely discontinued study drug plus 37 days).
  - o Treatment policy strategy for handling all other intercurrent events.
- Population-level summary: the percent reduction relative to placebo decline (the proportional treatment effect), comparing each dose level to placebo.

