#### 7.1.3.2 Safety and PD Biomarker Data

Depending on the statistical analysis method, a single value may be required for each analysis visit window (e.g., CFB by visit usually requires a single value), except for ">90 Days Post Last Dose" analysis visit window.

For safety data, if multiple valid, non-missing, continuous records exist in a post-baseline analysis visit window, records will be chosen based on the following rules if a single value is needed, unless otherwise specified:

- The record closest to the target day (in terms of days) for that visit will be selected.
- If there are multiple records that are equidistant from the target day (in terms of days), the later record will be selected.
- If there are multiple records on the same day (regardless of time), the average value will be taken.

For exploratory PD biomarker data, if multiple valid, non-missing, continuous records exist in a post-baseline analysis visit window, then the average value of these records will be taken.

For safety and exploratory PD biomarker data, if multiple valid, non-missing, categorical records exist in a post-baseline analysis visit window (not applicable to categorical measurements derived from continuous measurements), records will be chosen based on the following rules if a single value is needed, unless otherwise specified:

- The record closest to the target day for that visit (in terms of days) will be selected.
- If there are multiple records that are equidistant from the target day (in terms of days), the later record will be selected.
- If there are multiple records on the same day, the record with the worst severity will be selected, for example:
  - o higher grade severity will be selected over lower grade severity for toxicity grades;

Protocol No. AL002-2 Last Revision Date: 12 Aug 2025

- o "low" or "high" will be selected over "normal" for a test or exam with those categories;
- o "abnormal" will be selected over "normal" for a test or exam with those two categories;
- o "positive" will be selected over "negative" for a test or exam with those two categories.

For those categorical measurements derived from continuous measurements, if multiple valid, non-missing, continuous records exist in an analysis visit window, the rules for selecting a single value for continuous measurements apply first, then the corresponding categorical measurements will be derived based on the single selected continuous measurements.

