#### 7.7.1 PD Assessment Objective

#### 7.7.1.1 FAS

For exploratory PD biomarkers (CSF, plasma, amyloid PET, Tau PET and volumetric MRI) listed in Table 7-25 [subsets 1 and 2] in the FAS, their visit values, change from baseline (CFB) and percent change from baseline (PCFB) for the main estimand will be summarized by treatment group over time (all visits) using descriptive statistics (Table 7-26).

Comparisons of CFB between AL002 dose groups vs. placebo will be explored for the main estimand using MMRM models (see Section 7.4.1.2) with treatment group, categorical visit, visit-by-treatment interaction, baseline biomarker, and APOE e4 status of e4 carrier vs. non-e4 carrier as fixed effects (Table 7-26). Treatment comparisons will be reported for specified visits as indicated below:

- Plasma biomarkers:
  - O AD-pathology (Aβ42/40, pTau217, MTBR-Tau243): week 12, 24, 48, 72 and 96
  - o AD-pathology (pTau181): week 16, 36, 60 and 84
  - o Target engagement (IL1RA): week 1, 2, 4, 6, 8, 12, 24, 36, 48, 72 and 96
  - o Neurodegeneration (NfL, GfAP): week 12, 24, 48, 72 and 96
- CSF biomarkers: week 6, 48 and 72
- Amyloid PET parameters: week 48
- Tau PET parameters: week 48 and 72
- Volumetric MRI parameters: week 48, 72 and 96

Additionally, the same analysis for the main estimand described above will be repeated with the following groups in the model: AL002 15 mg/kg group, AL002 40 and 60 mg/kg combined group, and placebo group. All statistics described above from fitting the MMRM model will be reported only for the AL002 40 and 60 mg/kg combined group (or its comparison to placebo).

For Tau PET parameters [subset 1] in Table 7-25, a sensitivity analysis (main estimand) will be conducted with similar descriptive summaries and MMRM models for the subset with redefined baseline (either pre-dose Tau PET if evaluable or the first post-dose evaluable Tau PET scan if pre-dose PET scan

Protocol No. AL002-2 Last Revision Date: 12 Aug 2025

is missing) (Table 7-26). A pMMRM model (main estimand) will be additionally conducted for both subsets of true baseline and redefined baseline (Table 7-26).

Given the limited sample size mapped to the Week 96 analysis visit for CSF, Amyloid PET and Tau PET, this visit will only be summarized descriptively and excluded from modelling (i.e., pMMRM and MMRM).

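### Plasma samples from the safety follow-up of completers who do not enter the extension study count as on-treatment values at Weeks 60 to 96 (exploratory PD analyses only)

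*SAP*

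**What the plan says.** **Sampling.** In Protocol Table 9 (Section 14.1), the row that begins "Plasma sample for PD" is marked at Week 97, at the SFU and at early termination, but not at the efficacy follow-up. Protocol 3.3.4 sets the timing: "an SFU visit will follow 8 weeks after this last treatment period visit, unless the participant enrolls in the AL002-LTE study".

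**Allocation.** SAP 7.1.1.2.3 states that "Biomarker data will be allocated to analysis visits corresponding to the analysis visit window intervals in which they fall in". In Table 7-15 the late plasma windows are days 380–463 (Week 60), 464–547 (Week 72), 548–631 (Week 84) and 632 onward (Week 96). If several continuous PD records fall in one window, SAP 7.1.3.2 says "then the average value of these records will be taken".

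**Cutoffs.** There are two. SAP 6.2.1.2 applies to early stoppers: "data will be considered missing after a participant prematurely discontinued study drug plus 37 days". SAP 7.1.1.2.2 sets a limit of last dose plus 90 days, for safety and PK data only.

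**Estimand and reporting.** SAP Table 2-1 gives the PD endpoints attributes similar to those of the primary estimand, whose treatment condition is being on study treatment. SAP 7.7.1.1 lists the plasma comparisons to report, for example "Target engagement (IL1RA): week 1, 2, 4, 6, 8, 12, 24, 36, 48, 72 and 96". It keeps Week 96 out of modelling for CSF and PET because few samples map there. It makes no such exception for plasma.

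**The concern.** A plasma sample taken 56 days after the last dose is set to missing for a participant who stopped early. The same sample is kept, under an on-treatment visit label, for a participant who finished. That conflicts with an estimand defined on treatment.

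What is at stake is how the late plasma results are read. SAP Section 13 records that plasma sTREM2 was dropped because AL002 interferes with the assay. IL1RA is then the only plasma marker that Table 7-25 labels as TREM2 engagement. If its effect reverses off drug, washout values at Weeks 72 and 96 would pull the active arms toward placebo and could be mistaken for waning engagement. The same values feed the plasma/CDR-SB correlation models (SAP 7.7.2) and the pTau217-tercile analyses (SAP 7.7.3). LTE entry happens after randomisation, so the share of SFU values could also differ by arm.

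**Working it through.** **1. Reproduce the plan's schedule.** Screening 8 + predose baseline 3 + treatment 96 + SFU 8 = 115 weeks, as Protocol 3.2 states. Doses: 96/4 + 1 = 25, as Protocol 3.1.4 states. So the last possible dosing visit is Week 97, and its SFU comes 56 days later.

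**2. Map each final visit.** Study day = 7 × (week − 1) + 1, and SFU day = that day + 56. Reading Table 7-15:

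| Final visit (week) | SFU study day | Analysis visit | Other scheduled plasma sample in that window |
|---|---|---|---|
| 49, 53, 57 | 393, 421, 449 | Week 60 | none |
| 61, 65, 69 | 477, 505, 533 | Week 72 | none |
| 73, 77, 81 | 561, 589, 617 | Week 84 | none |
| 85, 89, 93 | 645, 673, 701 | Week 96 | none |
| 97 | 729 | Week 96 | Week 97 (day 673) |

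Moving the SFU by 5 days either way changes no row. In 12 of the 13 cases the SFU sample is the only scheduled plasma value in its window, so it becomes the visit value. Averaging occurs only for a Week 97 final visit.

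**3. Test the cutoffs.** Since 56 > 37, the 37-day rule would exclude the sample, but it applies only after premature discontinuation. Since 56 < 90, the 90-day cap would not exclude it even if it covered PD data.

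**4. Exposure at the SFU.** Protocol 1.4 gives a "terminal half-life of 9.0 days at an IV dose of 15 mg/kg and 9.1 days at an IV dose of 60 mg/kg" in healthy volunteers. Elapsed half-lives are 56/9.0 = 6.22 and 56/9.1 = 6.15. On-treatment plasma is collected before dosing (Table 9), about 28 days after the previous dose. The fair comparison is therefore SFU to trough: 2^(−56/t) ÷ 2^(−28/t) = 2^(−28/t), which is 0.116 at t = 9.0 and 0.119 at t = 9.1, or about 12%. This assumes a single exponential decline.

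**5. Which reported results are exposed** (SAP 7.7.1.1 and Table 7-27):
- IL1RA, pTau217, Aβ42/40, NfL and GFAP: Weeks 72 and 96.
- pTau181: Weeks 60 and 84.
- Plasma/CDR-SB correlation models: Weeks 72 and 96.

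Week 48 and earlier are clear, because the earliest completer SFU is day 393 and the Week 48 window ends at day 379.

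**6. Size.** Let f be the fraction of a marker's treatment effect lost by the SFU. The documents do not give f. An averaged value keeps (1 + (1 − f))/2 = 1 − f/2, and an SFU-only value keeps 1 − f.

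| f | Averaged (Week 97 completer) | SFU-only |
|---|---|---|
| 0 | 100% | 100% |
| 0.5 | 75% | 50% |
| 0.88 (effect tracks serum level) | 56% | 12% |
| 1 | 50% | 0% |

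These are per participant. If a share q of Week 97 attendees have an SFU, that group's mean Week 96 effect keeps 1 − q·f/2. At q = 0.5 this runs from 100% (f = 0) to 75% (f = 1). SFU-only participants with final visits at Weeks 85–93 would lower it further.

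**The case against.** The strongest reply is that the allocation gap does not show bias. The documents give no offset rate for any of these plasma markers, and a serum half-life is not a biomarker half-life. A marker that does not move within 8 weeks is unaffected. This stands: attenuation is conditional on reversal.

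Scope is also limited. LTE entrants have no SFU, and every eligible, consenting participant is offered the LTE. Early stoppers are already handled by the 37-day rule. Target engagement is also assessed through CSF sTREM2, modelled at Weeks 6, 48 and 72. The endpoints are exploratory with no multiplicity control (Protocol 8.3.3). All of this stands, and it limits the importance of the point.

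The timing of database lock is open. SAP Section 8 locks the data once all participants have completed or discontinued the planned treatment period, while Protocol 12.2 ends the study at the last visit, SFU included. Participants stopped by the common close have their SFU after the termination date, so some of those samples may miss the lock. Week 97 completers who finished at least 8 weeks before that date have theirs in time, so the averaging problem remains.

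A reader might infer a definite dilution figure for Week 96 by treating the 58% planned missingness at month 24 (SAP 3.5) as 42% attending Week 97 and assuming full reversal. The documents do not support that. The 58% is a planning value for CDR-SB, the LTE share is not stated, full reversal is only one end of the range, and a ratio of raw means is not the MMRM estimate. A reader might also cite about 1.4% of drug remaining at the SFU. That is relative to the post-dose level; against the predose samples actually compared, it is about 12%.

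**Conclusion.** The allocation rule is wrong as written for one group: participants who complete the planned treatment period and do not enter the LTE. Their SFU plasma sample is labelled as an on-treatment visit, and no rule removes it. This follows from the text and the schedule arithmetic without further assumption.

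The effect on results is conditional. It depends on how far each marker reverses in 8 weeks, how many completers skip the LTE, and whether the samples are in the locked data. None of these is given, so attenuation can be anything from nil to substantial. It would be unsafe to say that the AL002 effect is diluted at these visits, or that the primary analysis is affected. The correction should be made because it is nearly free and brings the derivation into line with the SAP's own estimand.

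**What to change.** In SAP 7.1.1.2.3 and Table 7-15, add a separate safety follow-up visit for plasma. Assign to it any sample collected at the nominal SFU visit, or later than 37 days after the end of the participant's planned treatment period. Summarise that visit descriptively, exclude it from the main-estimand MMRM and correlation models, and never average it with Week 96. The 37-day margin matches the horizon that SAP 7.4.1.4 already uses after the treatment period termination date.

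Keep the existing 37-day rule for premature discontinuation. Do not extend it to a cut at 37 days after the last dose for everyone. That would also drop scheduled treatment-period samples from participants whose dosing is paused and not resumed, and the estimand handles a pause short of discontinuation by treatment policy.

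The cost is a change of wording and derivation, with no new data. The downside is slightly fewer records at Weeks 60 to 96; those lost are off-drug samples.

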#### 7.1.2.3 Tau PET Measurement

Two definitions for baseline will be used for Tau PET (refer to Table 7-26 for analysis scope for PD biomarkers).

- *True baseline*: evaluable Tau PET scan result at Pre-dose Baseline visit prior to Study Day 1. If the Tau PET scan is not performed at the Pre-dose Baseline visit, then the baseline value is set to missing.
- Redefined baseline: evaluable Tau PET scan result at Pre-dose Baseline visit prior to Study Day 1
  if available or the first evaluable post-dose Tau PET scan result if pre-dose Tau PET scan is
  missing.

True baseline will be used in the main analyses for CFB. Redefined baseline will be used in the sensitivity analyses for CFB.

For participants who never received study drug administration, but were randomized, their data collected at the Screening visit will be used as the baseline value if needed (e.g., summaries of baseline characteristics on the ARS).

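### The redefined Tau PET baseline scan stays inside its own Week_R 48 window, so Week_R 48 change becomes 0, or half the real change, for participants without a pre-dose scan

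*SAP*

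**What the plan says.** Five rules in the SAP act together on Tau PET.

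- **Baseline, Table 7-19 (SAP 7.1.1.2.3).** Baseline_R is the pre-dose scan if there is one. "If not, then day of Week_R 48 nonmissing result (up to Day 421" is the fallback.
- **Baseline, SAP 7.1.2.3.** The fallback here is "the first evaluable post-dose Tau PET scan result if pre-dose Tau PET scan is" missing, with no upper day. The footnote to Table 7-19 likewise refers to the first post-dose visit and gives no limit.
- **Window, Table 7-19.** The follow-up row reads "Week_R 48 337 [2, 421"], the same interval as in the true-baseline Table 7-18.
- **Allocation, SAP 7.1.1.2.3.** "Biomarker data will be allocated to analysis visits corresponding to the analysis visit window intervals in which they fall in". Study day is the only criterion.
- **Several records, SAP 7.1.3.2.** For continuous PD biomarkers with more than one record "in a post-baseline analysis visit window, then the average value of these records will be taken".

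Treatment comparisons are reported for "Tau PET parameters: week 48 and 72" (SAP 7.7.1.1). The redefined baseline feeds descriptive summaries, MMRM and pMMRM (7.7.1.1) and a sensitivity version of the CDR-SB correlations (7.7.2). The supportive-estimand Tau PET analyses in 7.7.1.1 are specified on the redefined baseline only.

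Protocol 3.3.2 and the footnotes to protocol Table 9 allow a first Tau PET scan after dosing has begun, in some cases and with Sponsor agreement.

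**The concern.** The redefined baseline exists to bring in participants who have no pre-dose scan. For them, any scan on Days 2 to 421 that becomes Baseline_R also lies in the Week_R 48 window, and no rule removes it. It is then subtracted from itself, or from an average that contains it.

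Protocol Table 9 schedules Tau PET at the Predose Baseline Visit, Week 49 and Week 73, with a further scan at an efficacy follow-up or early termination visit if none was done in the preceding 24 weeks. A participant first scanned at Week 49 (analysis Week 48) therefore normally has one scan in the window. A participant given a late baseline scan soon after dosing, and then the Week 49 scan, has two.

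At stake is whether these analyses can do their job. A sensitivity analysis with built-in zeros cannot show whether the true-baseline result is robust, because agreement or disagreement may come from the derivation.

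**Working it through.** **Window limit.** Table 7-19 gives target Days 337, 505 and 673. The midpoints are (337 + 505)/2 = 421 and (505 + 673)/2 = 589. These reproduce the upper limits of Week_R 48 and Week_R 72, so Week_R 48 is an ordinary midpoint window with no adjustment for a scan used as baseline.

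**Rules applied to participants with no pre-dose scan.** The SUVR values are assumed for illustration.

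| Scans: day (SUVR) | Visit | First-scan baseline (7.1.2.3) | Week_R 48 result as baseline (Table 7-19) | Baseline scan excluded |
|---|---|---|---|---|
| 337 (1.30) | Week_R 48 | 1.30 − 1.30 = 0 | 0 | missing |
| 30 (1.20), 337 (1.30) | Week_R 48 | 1.25 − 1.20 = 0.05 | 1.25 − 1.25 = 0 | 1.30 − 1.20 = 0.10 |
| 337 (1.30), 505 (1.36) | Week_R 48 | 0 | 0 | missing |
| same | Week_R 72 | 1.36 − 1.30 = 0.06 | 0.06 | 0.06 |
| 30 (1.20), 337 (1.30), 505 (1.36) | Week_R 48 | 0.05 | 0 | 0.10 |
| same | Week_R 72 | 1.36 − 1.20 = 0.16 | 1.36 − 1.25 = 0.11 | 0.16 |

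The last column uses the first scan as Baseline_R. In general, with two scans x1 and x2 in the window and x1 as baseline, the change is (x1 + x2)/2 − x1 = (x2 − x1)/2.

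**Effect on the group mean.** Let q be the share of participants contributing a Week_R 48 value whose change is a structural zero, and m the mean change of the rest. The observed mean is (1 − q)m. If q is equal in two arms whose other participants differ by d, the unadjusted difference is (1 − q)d. For assumed q of 10%, 20%, 30% and 50%, this is 90%, 80%, 70% and 50% of d.

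If q differs by arm, the bias can go either way. Suppose there is no drug effect and mean change is positive:

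- q = 10% on placebo and 30% on active gives 1 − 0.7/0.9 = 22% apparent slowing;
- the reverse gives 1 − 0.9/0.7 = −29%, an apparent worsening.

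**Effect on variance.** If the other participants have variance s², the mixture has variance (1 − q)s² + q(1 − q)m². This is below s² only when (1 − q)m² < s². With q = 20%:

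- m = s gives 0.80 + 0.16 × 1 = 0.96 s²;
- m = 2s gives 0.80 + 0.16 × 4 = 1.44 s².

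The documents give neither m nor s for Tau PET.

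**First scan after Day 421, for example Day 505.** Under the Table 7-19 row there is no Baseline_R and no change value. Under SAP 7.1.2.3 that scan is Baseline_R and also falls in Week_R 72 [422, 589], giving a change of 0. The two rules conflict.

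**The case against.** The best defence is linguistic. SAP 5.3.1 requires both a baseline and a post-baseline measure for a change analysis, and the averaging rule is confined to post-baseline windows. On ordinary usage a scan serving as baseline is not post-baseline, so a sole scan would leave Week_R 48 change missing, which is the right answer. A careful programmer might do this unprompted.

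This does not settle the matter. The SAP nowhere says that the two measures must be different scans. Table 7-19 itself names the Week_R 48 result as the baseline while keeping Week_R 48 as a visit with its full window.

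Other parts of the defence stand:

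- Tau PET is optional and exploratory, and SAP 7.1.2.3 assigns the true baseline to the main analyses.
- Post-dose first scans are an exception needing Sponsor agreement, so a large q cannot be presumed.
- The two-scan case normally needs an early first scan outside the regular Tau PET schedule.
- MMRM and pMMRM adjust for baseline, so adjusted differences need not scale by exactly (1 − q).

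A reader might also infer that a first scan at Week 72 becomes its own follow-up. The documents do not establish that: it follows from 7.1.2.3 alone, while the Table 7-19 row rules it out.

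**Conclusion.** The point holds as a derivation error in the written rules. Followed literally, they give a Week_R 48 change of exactly 0 for a single post-dose scan in the window. For two scans they give half the real change or 0, depending on which baseline definition is used. Section 7.1.2.3 and the table footnote also conflict with the Day 421 limit in the table row.

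The attenuation factor (1 − q) rests on equal q across arms, unadjusted means and single-scan zeros. The q values above are assumptions.

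Three stronger inferences are not supported:

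- **That standard errors become too small.** The direction depends on the unknown ratio of mean change to its SD.
- **That attenuation equals the share of all Tau PET participants lacking a pre-dose scan.** What counts is the share among those contributing Week_R 48 values.
- **That the trial's main conclusions are at risk.** The CDR-SB efficacy analyses and the true-baseline Tau PET analysis are unaffected.

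The reach is the exploratory redefined-baseline analyses: descriptive summaries, MMRM, pMMRM and the CDR-SB correlation sensitivity analysis. The supportive-estimand Tau PET analyses deserve most attention, since no true-baseline counterpart is planned to check them against.

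**What to change.** In both Table 7-19 and SAP 7.1.2.3, including the table footnote:

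1. Use one definition of the post-dose Baseline_R scan, and state that this scan is excluded from every post-baseline window before any averaging.
2. State that only scans dated after Baseline_R count as follow-up. A participant with no later scan up to Day 421 then has a missing Week_R 48 change.
3. Apply the same upper day limit in each place.

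The change needs SAP wording and a small edit to the derivation code. The downside is that some participants drop out of the Week_R 48 summary; those with a Week 73 scan still contribute at Week_R 72. Re-counting follow-up time from Baseline_R is not needed for this correction. It is a debatable preference that would sit awkwardly with the matched timepoints in the CDR-SB correlations.
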